# Assessments.

Figure 2. Grid depicting when each assessment is obtained

rigare 2. Oria acpioning	when each assessment is obtained		Р	RE	DURING TREATMENT			Follo	OW-UP			
MEASURE	INSTRUMENT AND REFERENCES	Түре	BASELINE	LAB #1	WEEK 2	MONTH 1	MONTH 2	MONTH 3	LAB #2	6 Момтн	12 Month	BIOSENSOR
Screening Measures							ı		1			
Axis I Disorders	MINI Psychiatric Interview	Interview	*									
Binge-Eating Disorder	EDE Interview	Interview	*					*		*	*	
BMI	Weight, height	RA Eval	*	*	*	*	*	*	*	*	*	
Metabolic Measures	Lipids, HbA1c TSH (as needed)	Blood	*	*					*	*	*	
Safety Measures	Urine screen for pregnancy Urine drug test for opiates	Urine	*									
Menstrual Cycle Data	Menstrual cycle calendar, hormone use, reproductive and gynecological status	Interview	*		*	*	*	*		*	*	
Medical History	Clinical data, incl. start of new treatments	Interview	*					*			*	
Eating Behavior & Food C	Craving											
Eating Disorders	EDE-Q ELOCS	Self-Report	*		*	*	*	*		*	*	*
Eating Behavior	TFEQ YFAS	Self-Report	*			*	*	*		*	*	
Food Craving	Brief Questionnaire of Food Craving FCI-II	Self-Report	*	*		*	*	*	*	*	*	
Drive for Palatable Food	PFS Control of Eating Questionnaire	Self-Report	*	*		*	*	*	*	*	*	
Hunger	Hunger Ratings	Self-Report		*					*			
	Health and Behaviors	0 16 5	*		*	*	*	*	 	*	*	
Depression	Beck Depression Inventory-II	Self-Report	*	*	*	*	*	*	*	*	*	
Affect	Circumplex Scale	Self-Report		Î					Ŷ			+
Quality of Life	Perceived Stress Scale	Self-Report	*			-		*			*	*
Quality of Life	SF-12 Audit-2	Self-Report	*					*			*	
Alcohol Use	Godin Leisure Time Exercise Questionnaire	Self-Report	*					*			*	
Physical Activity Sleep		Self-Report	*	-		-		*			*	
Sieep	Pittsburgh Sleep Quality Index	Self-Report										
Safety & Compliance								 				
Adverse Events	SAFTEE Columbia Suicide Severity Rating Scale	Interview			*	*	*	*				
	Liver Function	Blood		*		*			*			

Page **12** of **49** 

Medication Compliance	Pill Counts	RA Count						*				
	Naltrexone and Bupropion levels	Plasma				*		*				
Vitals	Blood pressure and heart rate		*	*	*	*	*	*	*	*	*	
Placebo Rating	Placebo rating by clinician and participant	Self-Report				*		*				
Assays												
	Leptin, ghrelin, estrogen, progesterone	Blood		*					*			

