Monitoring depressive symptoms. Depressive symptoms will be monitored frequently. To monitor changes in depressive symptoms, patients will be asked to complete the BDI-II at all clinic visits (2x in first month, monthly thereafter). Research clinicians will review BDIs during the clinic visit, and will asked pointed questions pertaining to suicidality/suicidal ideation using the Columbia Suicide Severity Rating Scale. If it appears, based on the clinical judgment of the research clinician, that the participant is experiencing significant adverse effects of the medication, the investigators and study physician will be consulted and a determination of whether to discontinue the medication will be made. The participant will be compensated in full, and will be asked to continue to attend clinic visits and to continue to participate (if applicable) with the behavioral support to ensure remission of any distressing symptoms. If warranted, the participant will be given a referral. There is no assessment of suicidality in the Biosensor Arm.

Blood pressure and heart rate will be measured during all evaluation visits. Two readings will be taken at each assessment. In the event of systolic blood pressure  $\geq 160$  mm Hg and/or diastolic blood pressure  $\geq 100$  mm Hg, or an increase in heart rate of  $\geq 15$  bpm (from baseline), the study physician will be notified and will determine whether additional intervention and/or medication discontinuation is warranted.

Liver function will be measured during baseline, at month-1 clinic visits, and at the end of treatment. The study physician will review results of a full hepatic panel prior to the start of treatment and throughout treatment. Participants with hepatic disease will be excluded if this is detected at baseline, per exclusion criteria. Any changes and out-of-range values will be flagged immediately by research clinicians, and the study physician will determine whether additional intervention and/or medication discontinuation is warranted.

Wallet Safety Card. Each participant will be given a wallet card with the code number for the medication assignment in the event of an emergency and the need for breaking the blind. The research pharmacy has 24-hour service. Participants will be provided with contact information for the study physician and the PI, as well as emergency numbers in case of adverse events or other concerns. Research staff will have cell phones and can be reached 24/7.

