Because the projected effect sizes may not be large enough for detection during interim analyses, we are not proposing a preliminary analysis of accumulating efficacy and safety data by treatment assignment. Instead, we propose to submit semi-annual reports of aggregate data to the DSMB members that contains screening data, baseline demographics, retention data, serious adverse events data, as well as accrual status including projections, times to milestones, and any other data that will help in the assessment of the clinical trial. Based on this report, each DSMB member will complete a form making one of two recommendations: 1) continue recruitment as planned; or 2) schedule formal DSMB meeting immediately. If any DSMB member recommends a meeting, this will be scheduled within one week, minutes will be kept, the report will be

reviewed with the PI, and the committee will vote on whether the study should: 1) continue recruitment unchanged; 2) continue with a protocol amendment; 3) stop recruiting pending further investigation. If, after this meeting, any DSMB member votes to stop recruitment or requests a protocol modification, the Yale IRB will be informed.

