### 13. **Statistical Considerations:** Describe the statistical analyses that support the study design.

Baseline demographic and clinical characteristics for the randomized groups will be compared using chi-square tests for categorical variables, and ANOVA or Kruskal-Wallis tests for continuous variables. Continuous variables will be examined for normality using normal probability plots and Kolmogorov-Smirnov test statistics. If normality is not satisfied, transformations or nonparametric alternatives will be considered. Dropouts and completers will also be compared. Primary analyses will be based on an intent-to-treat basis. Primary outcomes will be tested at the two-sided alpha 0.05 threshold. Secondary analyses will be adjusted for multiple tests using the Bonferroni correction basing the adjustment on the number of conceptually related statistical tests within each hypothesis.

Overall analysis strategy. Mixed-effects models [92] will be used to compare treatments. These models allow for different numbers of observations per subject, use all available data on each subject, and are unaffected by randomly missing data. A further advantage is the capacity to test and account for individual-difference contributions to the treatment outcomes (Cudeck, 1996; Cudeck & Klebe, 2002; Hedeker et al., 1996; Hedeker & Gibbons, 1996; Singer, 1998). They provide flexibility in modeling the correlation structure of the data. In models for each outcome in Aims 1 & 2, we will include obesity status (obese vs. non-obese) and treatment (NB vs. placebo) as between-subject effects, time (see Aim-specific study time points) as a within-subjects factor, and subject as the clustering factor. Across analysis, time-points associated with the 12-week treatment phase will be considered as primary outcomes, and all analyses will be repeated to examine change

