during the 12-month follow-up period. All possible interactions will be modeled and the following primary a priori contrast will be tested: 1) placebo NB vs. active NB. Least-square means will be plotted and compared post-hoc to interpret significant effects. Because we cannot a priori predict the shape of the response over time in each arm of the trial we will first treat time as a categorical predictor and will then test for polynomial trends over time. We will consider different error structures (e.g., AR1, CS, independence) and select the best fitting one based on Schwartz' Bayesian Criterion (BIC). We will compare dropout patterns between groups and if there are concerns of informative dropout or informative intermittent missing data, we will use pattern mixture models [93] to perform sensitivity analyses. Secondary models will include subjects with complete data. To test for assessment reactivity, we will evaluate whether biosensor assessment (yes/no; between-subject variable) moderates our primary outcomes in Aim 1 (as either a main effect, or interacting with medication). If this is found, then all subsequent analyses for Aims 1 & 2 will be limited to the sample (n=140) without the biosensor assessment.

Primary Aim 1. We will use the mixed models described above to test the effectiveness of NB medication for BED patients with and without obesity. The primary aims are to evaluate NB medication for (a) reducing binge eating frequency; and (b) in the patients with obesity, for reducing % weight loss. Significant NB main effects (regardless of obesity status) on frequency of binge eating will be considered supportive of our primary hypothesis. We also expect that NB will be associated with significantly greater reductions in % weight loss among the BED+obese group. In view of the factorial design, we will also be able to assess whether obesity status moderates reductions in binge eating frequency. These analyses will focus on 12-week outcomes. Secondary analysis will be repeated to examine change during the 12-month FU period.

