Secondary Aims. (a) Explore effectiveness of NB medication for BED patients with and without obesity on secondary outcomes: eating-disorder pathology (EDE global), eating behaviors (EDE, TFEQ, FCI, PFS), depression (BDI-II), psychosocial functioning (SF-36), metabolic measures (lipid profiles, HbA1c, blood pressure, heart rate) and "remission" and "relapse" from binge eating behaviors. The continuous secondary outcomes (e.g., EDE global, BDI-II, SF-36) will be analyzed using the same approach as for primary aim 1, and logistic regression will be used to compare proportion achieving remission from binge eating or relapse to binge eating. (b) Explore predictors, moderators, and mediators of primary outcomes (i.e., binge eating). In terms of treatment processes, we will attempt to replicate our findings regarding the prognostic significance of rapid response for behavioral and pharmacologic treatments ([name] et al., 2006, 2012, 2015; Masheb & [name], 2008). We will follow Kraemer's (2002) conceptual/statistical models for exploring predictors, moderators and mediators for binge eating. Per [name] et al. (2012), we hypothesize that overvaluation of shape/weight and depression levels to be significant predictors; such findings would inform future treatment prescription regarding this pharmacologic intervention. Per Kraemer (2002), we will explore if baseline characteristics predict/moderate treatment effects by testing for main effects and interactions in models specified above for primary outcomes. In terms of mediators, we will explore whether differential symptom changes during treatment are associated with subsequent longer-term primary outcomes. Repeated assessments of eating behaviors (EDEQ and TFEQ scales), and food-reward constructs (FCI, PFS) relevant to putative mechanisms of action for NB, will yield relevant change variables for analyses of mediation (i.e. testing subsequent changes in binge eating).

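### Blood pressure and heart rate, safety measures for naltrexone/bupropion (NB), are analysed only as secondary effectiveness outcomes and appear to fall under the Bonferroni rule

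*Combined protocol and SAP*

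**What the plan says.** The safety role is stated in four places.

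- Measures lists blood pressure and heart rate under Safety and Compliance.
- Section I, item 10 (Risks) says they need monitoring because an earlier obesity trial found NB less favourable than placebo. Mean changes were −0.4 vs −2.1 for systolic pressure, −0.1 vs −1.0 for diastolic pressure and 1.0 vs −0.1 for pulse.
- Section I, item 11 (Minimizing Risks) sets action levels: systolic ≥160 mm Hg, diastolic ≥100 mm Hg, or a heart-rate rise ≥15 bpm from baseline. "Two readings will be taken at each assessment", and if a level is met "the study physician will be notified and will determine whether additional intervention and/or medication discontinuation is warranted".
- Section II, Drugs/Biologics (Risks) repeats the label precaution.

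The assessment grid (Figure 2, row "Blood pressure and heart rate") schedules them at baseline, week 2, months 1, 2 and 3, both laboratory sessions and both follow-ups.

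In the statistical section (item 13) they are named once, under Secondary Aims (a), as "metabolic measures (lipid profiles, HbA1c, blood pressure, heart rate"), among outcomes for exploring effectiveness. Continuous outcomes there use the Aim 1 mixed model, in which "we will first treat time as a categorical predictor and will then test for polynomial trends over time". On multiplicity, "Secondary analyses will be adjusted for multiple tests using the Bonferroni correction". The same sentence then says how large the family is to be, "basing the adjustment on the number of conceptually related statistical tests within each hypothesis". No safety exemption is given, and item 13 contains no by-arm count of participants meeting the action levels.

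For the period of the trial, the monitoring plan (item 12) says "we are not proposing a preliminary analysis of accumulating efficacy and safety data by treatment assignment".

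**The concern.** A multiplicity correction guards against false claims of benefit. Applied to a measure where the known drug effect is unfavourable, it works the other way: it raises the bar for flagging harm, and a real rise becomes more likely to be reported as not significant.

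The rule also has no fixed size here. It counts related tests within a hypothesis, but Secondary Aims (a) states no hypothesis for these measures. The threshold for a blood-pressure or heart-rate result is therefore open, and could be settled after the data are seen.

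Because no by-arm safety analysis is proposed during the trial, the final analysis is where a comparison of the arms on these measures has to be made and interpreted.

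**Working it through.** The plan gives no SD, power or family size for these outcomes, so there is no stated figure to reproduce.

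**Inputs from the documents.** Two-sided alpha 0.05 (item 13, stated for primary outcomes). 50 per cell, so 100 per arm. Attrition of 20–38% in earlier drug studies of binge-eating disorder (item 12); 30% gives 70 per arm. Pulse difference 1.0 − (−0.1) = 1.1 bpm (item 10).

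**Assumptions.** SD of heart-rate change 8–10 bpm. Family size k:

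- k = 1: heart rate alone.
- k = 3: systolic, diastolic and heart rate.
- k = 4: the measures as listed in Secondary Aims (a).
- k = 8: four lipids (as itemised in Measures), HbA1c, systolic, diastolic and heart rate.

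**Step 1: growth in the detectable difference.** Ratio at 80% power = (z(1 − 0.025/k) + 0.8416) / (1.9600 + 0.8416).

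| k | alpha per test | z | ratio | increase |
|---|---|---|---|---|
| 1 | 0.05 | 1.9600 | 1.000 | 0% |
| 2 | 0.025 | 2.2414 | 1.100 | 10% |
| 3 | 0.0167 | 2.3940 | 1.155 | 15% |
| 4 | 0.0125 | 2.4977 | 1.192 | 19% |
| 8 | 0.00625 | 2.7344 | 1.276 | 28% |

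**Step 2: observed heart-rate difference needed for significance at one visit.** z × SD × √(2/n), a two-sample approximation to the model contrast.

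| SD, n per arm | SE | k = 1 | k = 4 | k = 8 |
|---|---|---|---|---|
| 8, 100 | 1.131 | 2.22 | 2.83 | 3.09 |
| 8, 70 | 1.352 | 2.65 | 3.38 | 3.70 |
| 10, 100 | 1.414 | 2.77 | 3.53 | 3.87 |
| 10, 70 | 1.690 | 3.31 | 4.22 | 4.62 |

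An observed difference of 2.5 bpm has p = 0.027 in the first row: it passes 0.05 and fails 0.0125. That is the best case. In the other three rows p = 0.064, 0.077 and 0.139, so the result misses 0.05 without any correction.

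**Step 3: power at the cited effect.** With a true difference of 1.1 bpm, power runs from 16% (SD 8, n = 100: 1.1/1.131 = 0.97 SE) down to 10% (SD 10, n = 70: 1.1/1.690 = 0.65 SE) uncorrected. With k = 4 or 8 it is 2–6%. Non-significance is the likely result either way.

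**Step 4: what a count of action-level crossings would show.** Assume normal changes with the means cited in item 10. A rise ≥15 bpm at one visit then has probability P(Z ≥ 15.1/SD) on placebo and P(Z ≥ 14/SD) on NB.

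- SD 8: 3.0% vs 4.0%, a difference of about 1.0 point.
- SD 10: 6.6% vs 8.1%, a difference of about 1.5 points.
- The 95% half-width, 1.96 × √(p0q0/n + p1q1/n), runs from 5.1 points (SD 8, n = 100) to 8.6 points (SD 10, n = 70).

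For any crossing over four clinic visits, assume an exchangeable multivariate normal distribution:

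- SD 8, within-person correlation 0.7: 7.6% vs 9.9%, half-width 7.8 points at n = 100.
- SD 10, within-person correlation 0.3: 20.7% vs 24.7%, half-width 13.9 points at n = 70.

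Over two visits the placebo figure is only 4.9–12.0%, so an ever-crossed count depends on visits attended. For a general shift the counts tell less than the mean differences.

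**The case against.** **The rule may not apply, or may apply with a small family.** The aim is exploratory, states no hypothesis, and heart rate need not be conceptually related to lipids or HbA1c. This stands in part. It is why the size is 0–28% and not only 19–28%, and why the coverage is the natural reading and not a certain one. Against it, item 13 contrasts secondary analyses with primary outcomes and exempts nothing.

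**The dual role is legitimate.** Blood pressure and heart rate can be cardiometabolic outcomes of an anti-obesity drug as well as safety measures. This stands: listing them as secondary outcomes is not itself an error. What is missing is a statement of the safety role in the analysis and of how it bears on the correction.

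**Correction rarely decides the result.** At the cited pulse effect, power is low with or without it. This also stands, and it argues for intervals over tests.

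**A stronger reading: that the plan has no by-arm safety comparison of these measures.** The documents do not support it. The mixed model compares the randomised arms and, with time categorical, can give NB–placebo differences at week 2 and months 1, 2 and 3. Individual safety is handled separately, by physician notification, adverse-event interviews and review by the monitoring board.

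**Another tempting inference: that a final by-arm table of action-level crossings is ruled out, or that its absence is an error.** The monitoring plan declines only by-arm analysis of accumulating data. A final table is unplanned, not prohibited, and its expected precision makes it optional.

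**Conclusion.** The concern holds as a modest point about analysis and reporting. Following the plan on its natural reading subjects two recognised NB safety measures to a correction meant for efficacy claims, with a family size that nobody can state in advance. The consequence is limited to significance labels: the detectable difference grows by 0–28% for families of 1 to 8 tests, while estimates and ordinary 95% intervals do not change.

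The percentages depend only on the assumed family size and 80% power. The bpm and power figures also rest on an assumed SD of 8–10 bpm and 70–100 per arm, and the crossing rates on normality and assumed within-person correlations of 0.3–0.7. None of these assumptions affects the textual finding. Confidence is medium, because the coverage of the Bonferroni rule is inferred. The change is worth considering because it costs almost nothing.

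**What to change.** In item 13, in the multiplicity paragraph and Secondary Aims (a), state that blood pressure and heart rate are also safety outcomes and are exempt from Bonferroni. Report the mixed-model NB–placebo differences at week 2 and months 1, 2 and 3 with unadjusted 95% confidence intervals, and state that a non-significant difference will not be read as absence of harm.

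Optionally, add a descriptive by-arm table of participants meeting the item 11 action levels at those four scheduled clinic visits:

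- Apply the same reading rule that triggers physician notification. Item 11 calls for two readings but does not say whether either one or their mean counts, so the rule should be written down.
- Exclude laboratory-session vitals or show them separately. Those sessions are optional, include repeated readings, and some first sessions fall on treatment at weeks 4–6.
- Give the number assessed as the denominator.

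The cost is a wording change and at most one table from data already collected, with no effect on the primary analysis. The downside is no family-wise error control for these comparisons. The counts would be imprecise and would supplement the mean differences, not replace them.

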Overall, several medications have short-term efficacy relative to placebo [20] and certain psychological treatments have efficacy [21] with important advantages over medication (alone or in combination) [20].

Pharmacotherapy for BED has received research attention, albeit nearly all RCTs have been of short duration and without follow-up period to establish durability [20, 22, 23]. Critical review and meta-analysis show that

several drugs – working through varied mechanisms – have short-term efficacy relative to placebo for reducing binge eating and produce weight loss ranging from modest to none [20]. Placebo-controlled trials of anticonvulsants topiramate and zonisamide [24-26] have reported effects for reducing both binge-eating and weight (average weight loss of roughly 3-4 kg compared to placebo), but have also shown high dropout and frequent adverse events that become near-universal and troubling with longer use [27]. SSRI antidepressants, initially regarded as a potential treatment strategy [e.g., 28] are characterized by small effect sizes relative to placebo [20], produce no weight loss at all [29] and are inferior to CBT [29, 30].

Lisdexamfetamine dimesylate (LDX) for BED. An important development was the FDA approval in January 2015 of a CNS stimulant, LDX, for the treatment of moderate-to-severe BED. Approval was based on findings from an integrated series of studies funded by the manufacturer. The phase II RCT demonstrated that 50mg and 70mg were superior to placebo [31, 32] for reducing binge-eating days and reported binge-eating abstinence rates of LDX versus placebo (Study 1: 40% versus 14%; Study 2: 36% versus 13%) at the end of the 11-week treatments. Importantly, no longer-term follow-up are presently available.

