### Procedures for providing follow up care:

Medical monitoring will occur at all clinic and follow up visits and medical care will be provided if warranted. If a study participant experiences any psychiatric symptoms or distress (e.g., depressive symptoms or

suicidality) at any stage of study participation he/she will receive short-term treatment and support from the study treatment team (including psychologists and a psychiatrist) and will be connected to a local emergency department (e.g., the Crisis Intervention Unit at Yale-New Haven Hospital) and his/her physician or therapist for ongoing care.

Measurement and reporting of subject accrual, adherence to inclusion/exclusion criteria.

Review of the rate of subject accrual and adherence to inclusion/exclusion criteria will occur regularly by the PI and co-Investigators and yearly by the DSMB. These reviews will help to assure that participants meet eligibility criteria and ethnic diversity goals outlined in the grant proposal.

Measurement and reporting of participant treatment completion rates.

Participation rates (retention and attrition) will be reviewed on an ongoing basis by the PIs and co-investigators to identify any potential problems, and formally by the PIs and DSMB semi-annually. Any differential dropout across blinded study groups and/or higher than expected dropout will be reviewed by the investigators to determine whether any problems are present and what, if any, corrective action needs to be taken.

During the reviews, if the DSMB has concerns about whether attrition has reached a level that might inhibit the ability of the study to address its primary aims, they will suggest a meeting to discuss methods for improving subject retention. Previous pharmacotherapy studies for BED (with comparable time frames for pharmacotherapy) have reported attrition rates between 20% and 38%. Studies of bupropion for obesity treatment reported attrition of 30% to 38%. Thus, "trigger points" for review and discussion by principal investigator and research staff will be: 35% ("low alert"), 40% ("mid alert"), 45% ("high alert"), 50% ("extreme alert"). With early alerts to problems, action would be taken to avoid higher level alerts; if a higher-level alert should arise, more drastic actions would be taken.

The following actions would be taken at each level of alert:

- (1) Low-level alert = Review of potential problems by PI.

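### The planned between-arm test of relapse depends on remission after randomisation, so neither natural denominator gives an interpretable comparison; sustained remission over all randomised participants would be better

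*Combined protocol and SAP*

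**What the plan says.** The Secondary Aims paragraph of the combined protocol and SAP (Section I, item 13, Statistical Considerations) lists remission and relapse among the secondary outcomes to be explored. It states that "logistic regression will be used to compare proportion achieving remission from binge eating or relapse to binge eating". It does not define either event or give a time point, denominator or missing-outcome rule.

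Other parts of the document fix the setting:

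- The inclusion criteria (item 8) require a current diagnosis of binge-eating disorder at entry.
- Hypothesis 1.1 (item 1) expects the drug to reduce binge eating more than placebo.
- The assessment grid (Figure 2) repeats the Eating Disorder Examination (EDE) interview at month 3 and at the 6- and 12-month follow-ups.
- The design overview (item 4) gives durability of the medication effect as the reason for the 12-month follow-up.
- Item 13 describes the mixed models for continuous outcomes as ones that "use all available data on each subject, and are unaffected by randomly missing data". Those models are to be repeated over the follow-up period.

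**The concern.** Randomisation makes the arms comparable as randomised. It does not make the remitters in one arm comparable with those in the other. If the drug works, some participants remit on it who would not have remitted on placebo. Where those extra remitters are the harder cases, the drug arm's remitters carry a worse prognosis into follow-up and relapse more often, even if the drug has no effect on relapse.

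Using all randomised participants as the denominator for relapse restores comparability but not meaning. A participant who never remits cannot relapse, so the arm with fewer remissions gets the lower relapse rate.

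Either way, an effective drug can appear to promote relapse. Relapse is the binary outcome that speaks most directly to durability, so readers will look at it.

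**Working it through.** **No plan figure to reproduce.** The document gives no expected remission or relapse rate and no power for these outcomes. What follows is illustration.

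**Inputs**

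- 100 participants per arm: four cells of 50, allocated in equal proportions (items 1 and 4, and the randomisation paragraph).
- Remission 40% on drug and 14% on placebo. The Background (item 3) reports these for a different drug at 11 weeks, with 36% and 13% in a second study. Their use here is an assumption.
- Relapse of 30% among placebo remitters: an assumption.
- No drug effect on relapse at any given severity: an assumption, made to isolate the artefact.

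**Step 1: size of a remitters-only comparison.** 100 × 0.40 = 40 against 100 × 0.14 = 14 (36 against 13 with the second pair). Power for an assumed relapse of 25% versus 50% is 0.41 (0.39 with the second pair), compared with 0.96 if 100 per arm could be compared.

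**Step 2: how the artefact arises.** Suppose everyone who would remit on placebo would also remit on drug. Drug-arm remitters are then 14 such people plus 26 who remit only on drug. With relapse risks r1 and r2 in these two groups:

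relapse among drug remitters = (14 × r1 + 26 × r2) / 40; among placebo remitters = r1.

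- r1 = r2 = 30%: 30% versus 30%, so no artefact.
- r1 = 30%, r2 = 50%: (4.2 + 13) / 40 = 43.0% versus 30.0%, an odds ratio of 1.76 with no drug effect on relapse.

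**Step 3: a smoother version.** Give participants a normally distributed severity score. Model remission by a logistic function of severity calibrated to 14% and 40%. Model relapse by a second logistic function, identical in both arms and calibrated to 30% among placebo remitters. Vary the severity slope from 0.5 to 2 for remission and from 0.5 to 1.5 for relapse.

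- Excess relapse on drug: about 1 to 12 points across the grid, always in the same direction.
- Central slopes (1.5 for remission, 1 for relapse): 37% versus 30%.

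This range belongs to the model and is not a bound; the second case in step 2 gives 13 points.

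**Step 4: against sampling error.** At the central values the standard error of the difference is √(0.37 × 0.63 / 40 + 0.30 × 0.70 / 14) = 0.144. The 7-point gap is about half a standard error. Fisher's exact test at 0.05 would declare significant harm about 4% of the time, before the Bonferroni adjustment planned for secondary analyses.

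**Step 5: relapse over all randomised.** Take the no-artefact case, with 30% relapse among remitters in both arms: 0.40 × 0.30 = 12.0% on drug against 0.14 × 0.30 = 4.2% on placebo. The drug looks worse only because more of its participants had a remission to lose.

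**Step 6: sustained remission over all randomised.** In the same case: 0.40 × 0.70 = 28.0% against 0.14 × 0.70 = 9.8%. At the central values of step 3: 0.40 × 0.63 = 25.2% against 9.8%. All 100 per arm are in the denominator.

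**The case against.** The case against has four parts.

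- **The denominator is inferred.** The plan never says relapse will be analysed among remitters only. That is true, but the other natural reading, all randomised participants, fails for the reason in step 5. The difficulty does not depend on which was meant.
- **The artefact may be small or absent.** It requires severity to influence both remission and relapse, which the document does not establish. With equal prognosis it is zero, and at these numbers it would seldom produce a significant result. This stands and limits the weight of the point. It also shows that the planned test is weak as well as hard to interpret.
- **Durability does not rest on this test.** The mixed models of binge-eating frequency are repeated over the 12-month follow-up, and the binary outcomes are secondary and exploratory. This stands.
- **Sustained remission answers a different question.** Much of 28.0% versus 9.8% is the month-3 difference carried forward. This also stands, and is a reason to present the two outcomes together. It does not rescue the relapse test.

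**Conclusion.** The point holds for relapse. The planned between-arm regression either compares groups selected after randomisation or penalises the arm with more remitters. Under the stated assumptions the spurious excess of relapse on drug is about 1 to 12 points, with 37% versus 30% in the centre and none if remitters' prognosis is equal. The remission rates come from another drug, and the severity slopes and the 30% relapse rate are assumed. This is an inexpensive improvement to a secondary analysis; the primary test of binge-eating frequency is untouched.

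Three stronger readings are tempting, and the documents do not support them.

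- **That the remission comparison leaves out dropouts.** No section says so. Section VI, item 2 invites dropouts back for the follow-up evaluations. The sentence "Secondary models will include subjects with complete data" sits within the general mixed-model strategy and does not set the remission denominator.
- **That the plan contradicts its own intent-to-treat commitment.** The commitment is "Primary analyses will be based on an intent-to-treat basis", and remission and relapse are secondary.
- **That neither comparison is randomised.** Remission over all randomised participants would be a randomised comparison, and nothing rules it out.

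The unstated denominator and missing-outcome rule for remission are therefore missing detail and no more.

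**What to change.** In the Secondary Aims paragraph of item 13:

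1. Define remission and relapse and give their time points.
2. Replace the relapse regression with sustained remission: remitted at the month-3 EDE interview and still remitted at both the 6- and 12-month interviews. Use all randomised participants as the denominator and compare the arms by logistic regression. Requiring the 6-month interview avoids counting someone who relapsed and recovered by month 12 as sustained.
3. Report relapse among month-3 remitters by arm as numbers and percentages, without a test, noting that the groups are selected after randomisation.
4. Present sustained remission beside month-3 remission.

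While editing, name the analysis set and missing-outcome rule for these binary outcomes, with a sensitivity analysis under a different assumption. Counting missing as not remitted should not be the only rule. If true remission were 25% in both arms and equally common among dropouts, and 38% were missing on drug and 20% on placebo (an assumed split; the document gives 20% to 38% only as a range across earlier studies), that rule would show 0.25 × 0.62 = 15.5% against 0.25 × 0.80 = 20.0%.

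The cost is SAP wording, since the interviews are already scheduled. The price in interpretation is that no single test then isolates durability from acute response.
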